#### **Biostatistical Analysis**

## Detailed Protocol: SAGE

We will mainly use MANCOVA methods to compare the different conditions while controlling for various background factors, such as age and baseline cognitive performance. Cognitive change scores will be the main outcome variables. In addition, we will analyze changes from baseline in BDNF levels, gait score neural activity, as measured by ERPs, and degree of vascular coupling, as measured by TCDs.

In separate analyses, we will investigate whether various cognitive domains (e.g., executive functions, memory) are differentially affected by different types of stimulation. We will also perform separate analyses for closer investigation of how age, education, intelligence and mood may modify the experimental effects.

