### **Specific Aims**

The overarching goal of the current study is to identify factors that promote neural plasticity and cognitive health in elderly persons.

The specific aims address the impact of different types of structured mental or physical stimulation over a 5 week training period on the following:

1. Biological markers of brain plasticity (e.g., BDNF)
2. Electrophysiologic markers (event-related potentials) of neural efficiency and capacity
3. Neuropsychological markers of cognitive performance
4. Vascular markers of cerebral health (e.g., neurovascular coupling using transcranial doppler)

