### **Subject Selection**

We aim to have 200 subjects complete the study. There are two sites: one at BWH and one at Linnaeus University, Vaxjo, Sweden, with 100 subjects participating at each site.

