#### Gait

Gait will be assessed through a procedure in which subjects walk 10 meters under two conditions:

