#### Blood Samples

Subjects will be escorted to the phlebotomy lab at the BWH Center for Clinical Investigation, [name], which is in the same building as where our offices are located. They will be given the opportunity to sit quietly in the waiting area for ~10 minutes before being escorted to a phlebotomy room. Blood samples will be taken via a cannula inserted into a vein by a BWH phlebotomist. Approximately 35 ml of blood will be collected.

Approximately 10 ml of blood will be prepared according to the method recommended by the [name] Laboratory, Medical University of South Carolina.

In brief, one vacutainer tube with ~10 ml of whole blood is collected. This collection of blood will yield eight Eppendorf tubes with about 0.5 ml of serum in each. Another Eppendorf tube will contain the buffy coat (if available), and the vacutainer tube will contain the blood clot.

In the event that the BWH Center for Clinical Investigation is unavailable for blood processing and packaging, the sample will be taken to the Clinical Trial Center at BWH, where processing and packaging will be completed.

After freezing / storage, four of the Eppendorf tubes of serum, as well as one Eppendorf tube containing buffy coat, and the vacutainer tube containing the clot will be sent on dry ice by overnight mail to the [name] Laboratory, [name], Medical University of South Carolina, [name].

The remaining four Eppendorf tubes of serum will continue to be stored at BWH until the [name] Lab confirms receipt of the specimens. If the [name] lab does not require these tubes, they will be transported to the [name] Lab at Brigham and Women's Hospital and stored at BWH/Harvard-Partners Center for Genetics and Genomics, [name] (see below).

To prepare the serum, the blood first stays for 30 minutes at room temperature and is then centrifuged (at 4° C) for 10 minutes. The serum is then collected in a separate polypropylene container, mixed by inverting several times, and finally distributed into eight Eppendorf tubes, with 0.5 ml of serum in each. These will be kept frozen in Ziplock bags at -70° to -80°. The clot and the buffy coat (if available) will also be frozen and sent to the [name] Lab.

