### ERPs

Subjects will then participate in ERP experiments while data on brain waves are being collected. An ActiveTwo electrode cap (Behavioral Brain Sciences Center, Birmingham, UK) will be used to hold to the scalp a full array of 128 Ag-AgCl BioSemi (Amsterdam, The Netherlands) "active" electrodes whose locations are based on a pre-configured montage. Electrodes are arranged in equidistant concentric circles from the 10-20 system position Cz. In addition to the 128 electrodes on the scalp, 6 mini bio-potential electrodes will be placed over the left and right mastoid, beneath each eye, and next to the outer canthi of the eyes to check for eye blinks and vertical and horizontal eye movements. EEG activity will be digitized at a sampling rate of 512 Hz.

During the experimental protocols, visual or auditory stimuli will be presented. Participants will be asked to respond to designated stimuli by button press or foot pedal. Visual stimuli will include simple geometric shapes, letters, and complex figures that are presented on a high resolution monitor. Auditory stimuli will be presented binaurally at between 75dB SPL and 90dB SPL through high quality headphones.

The protocols will assess electrophysiological responses to novelty processing (subject-controlled novelty oddball task), working memory/attention (n-back task), and visual and auditory perception (visual and auditory evoked potential studies). Before beginning any new experimental condition, subjects will be given step-by-step explanations of what to do. Subjects will participate in practice trials. A brief break will occur between each block, and longer breaks will take place between each experimental condition.

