### Transcranial Doppler (TCD)

Information about blood flow using transcranial doppler (TCD), a non-invasive technique, also will be collected during an *n*-back task and in response to flashing checkerboard stimuli. TCD recordings will be done either before or after the ERP experiments.

Neurovascular coupling reflects the link between regional synaptic activity and regional cerebral blood flow. Under normal conditions, cerebral blood flow and cerebral metabolic rate are coupled, with an increase in metabolic demand leading to an increase in blood flow. Neurovascular coupling will be indexed by changes in bilateral middle cerebral artery blood flow velocities during the *n*-back task. A 2-MHz, pulsed flat transcranial Doppler probe (MultiDop, DWL) will be placed over each temporal bone. The signal on both probes will be range gated to a depth of 45 mm to 60 mm, to insure insonation of the M1 segment of the middle cerebral artery. Once the signals are maximized, the probe will be fixed in place for the duration of the test using a Velcro headband that will be placed over the ERP electrode cap. Localization and determination of the proper artery and position will be performed according to standard techniques. Normally, in about 1 out of 5 older people, these blood vessels cannot be tested.

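### Change in BDNF, gait, ERP and TCD: naming each measure's own baseline as a covariate, in a separate model per measure, is a cheap and optional gain in precision

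*Protocol*

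**What the plan says.** The Biostatistical Analysis section of the protocol plans mainly MANCOVA to compare the four conditions, "controlling for various background factors, such as age and baseline cognitive performance". Cognitive change scores are the main outcome. For the additional outcomes it states "we will analyze changes from baseline in BDNF levels", and continues with gait, ERP activity and vascular coupling by TCD. BDNF, ERP and TCD serve aims 1, 2 and 4 under Specific Aims.

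All four kinds of measure are taken before training: "Gait will be assessed through a procedure in which subjects walk 10 meters under two conditions" (Gait), "Approximately 35 ml of blood will be collected" (Blood Samples), "Subjects will then participate in ERP experiments while data on brain waves are being collected" (ERPs) and "Neurovascular coupling will be indexed by changes in bilateral middle cerebral artery blood flow velocities" (Transcranial Doppler). The Post-Intervention Assessment section repeats each of them.

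On size, Subject Selection states "We aim to have 200 subjects complete the study", half of them at each of two sites. The Randomization section lists four arms and gives no allocation ratio. The TCD section warns that about one older person in five cannot be measured.

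**The concern.** The one baseline score named as a covariate belongs to the cognitive outcomes. Nothing comparable is named for BDNF, gait, ERP or TCD. If the examples were taken as the full covariate set, each of these change scores would be modelled without its own starting value. Baseline cognition would stand in for that value only as far as the two are correlated.

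A raw change score fixes the slope of the post value on the baseline at 1. Where the true slope is lower, the baseline still explains part of the change, and leaving it out makes the contrasts noisier than they need be. The stake is confined to precision on the additional outcomes. TCD is the thinnest of them, because some subjects yield no measurement.

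**Working it through.** The protocol gives no pre-post correlation, SD, significance level or power for these measures, so there is no figure of its own to reproduce.

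**Inputs from the protocol:** 200 completers, 100 per site; four arms; TCD obtainable in about 80%, so about 160.

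**Assumed:** pre-post correlation ρ from 0.3 to 0.9; ratio of post to pre SD k of 0.8, 1 or 1.25; correlation c = 0.3 between baseline cognition and the marker's baseline, with cognition related to the post value only through that baseline.

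**Step 1, variance per subject, in units of the pre SD squared.**
- Change score: 1 + k² − 2ρk.
- Adjusted for own baseline: k²(1 − ρ²).
- Cut = 1 − (adjusted / change). At k = 1 this is 1 − (1 − ρ²)/[2(1 − ρ)] = (1 − ρ)/2.
- Example at k = 1, ρ = 0.5: change 1.00, adjusted 0.75, cut 25%.

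**Step 2, against a change-score model that already holds baseline cognition (k = 1).** Cut = 1 − (1 − ρ²)/[2(1 − ρ)(1 − c²(1 − ρ)/2)]. At ρ = 0.5: 1 − 0.75/0.9775 = 23%.

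| ρ | k = 0.8 | k = 1 | k = 1.25 | k = 1, cognition already in the model |
|---|---|---|---|---|
| 0.3 | 50% | 35% | 22% | 33% |
| 0.5 | 43% | 25% | 11% | 23% |
| 0.7 | 37% | 15% | 2% | 14% |
| 0.9 | 39% | 5% | 5% | 5% |

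At k = 1.25 and ρ = 0.8 the cut is nil, because the slope ρk is then exactly 1.

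**Step 3, simulation.** Four arms of 50, 4,000 runs, age and cognition in both models, k = 1: variance cuts of 32%, 23%, 14% and 4% at ρ = 0.3, 0.5, 0.7 and 0.9, with mean contrasts within 0.004 of zero. A second run of 8,000 per setting, without cognition, gave type I error of 0.047 to 0.054 with and without the own baseline.

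**Step 4, cost of m added baselines.** Variance inflation = 1 + m/(ν − m − 1), where ν = N − 4 arms − 1 for age.
- One baseline, 200 subjects (ν = 195): 1 + 1/193, or 0.5%.
- One baseline, TCD at 160 (ν = 155): 1 + 1/153, or 0.65%.
- One baseline, one site only: 100 subjects (ν = 95), 1 + 1/93, or 1.1%; TCD at 80 (ν = 75), 1 + 1/73, or 1.4%.
- In one joint MANCOVA all m baselines enter every equation. At ν = 195: 2.7% for m = 5, 5.4% for m = 10, and 1 + 20/174, or 11%, for m = 20.

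At k = 1 the break-even correlation is 2/inflation − 1. It is about 0.99 for one baseline, and 0.95, 0.90 and 0.79 for 5, 10 and 20 joint baselines, if the other markers' baselines explain nothing.

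**Step 5, detectable difference (80% power, two-sided 5%, no multiplicity correction, k = 1).** 2.802 × √(4(1 − ρ)/n) for change and 2.802 × √(2(1 − ρ²)/n) with own baseline, n per arm. At ρ = 0.5:
- n = 50: 2.802 × 0.200 = 0.560 SD, against 2.802 × 0.1732 = 0.485 SD.
- n = 25: about 0.79 against 0.69 SD.

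The first line needs equal allocation and the marker collected at both sites. The second applies, with equal allocation, if it is collected at one site only.

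**The case against.** The strongest case is that this is no finding at all. The covariates of each additional outcome model commonly belong in an analysis plan, which is not shown and may already name these baselines. The protocol's list is explicitly by example, and it already adjusts the main outcome for baseline. Nothing shows that the sponsor means to leave the marker baselines out. All of that stands, and it is why the point is optional.

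It is also fair that the size of the gain rests on assumed values. The range includes nil, and at k = 1.25 and ρ = 0.8 a simulation showed a loss of 0.4%. That baseline cognition substitutes poorly for a marker's own baseline follows from the assumed correlation of 0.3, not from the protocol.

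Two further objections shape the fix. First, a joint MANCOVA cannot give each outcome its own covariate. The protocol implies many measures (several ERP components and tasks, gait under two conditions, TCD on both sides), and 20 joint baselines would cost about 11%, cancelling the gain above ρ of about 0.8. A joint model with TCD baselines would also, on complete data, keep only subjects with usable TCD. Second, absolute detectable differences depend on which sites collect a marker. The procedures are described only for the Boston hospital, and the protocol does not say whether the Swedish site takes every measure.

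A reader might infer that the planned change-score contrasts are biased or invalid. The documents do not support that: assignment is randomised, and both analyses estimate the same contrast with the same type I error.

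**Conclusion.** The point holds as an optional improvement in precision. The plan as written is valid, does not contradict itself and permits the better analysis without asking for it. For equal SDs the variance of an arm contrast falls by 35% to 5% as ρ goes from 0.3 to 0.9. Across the SD ratios tried the gain runs from nil to about half. At ρ = 0.5 and k = 1, the net gain at 200 subjects equals about 33% more subjects (1/(0.75 × 1.0052) = 1.33).

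These percentages do not depend on the number of sites, apart from the small covariate cost. The detectable differences do depend on it and should be quoted only with their conditions. It would also go too far to conclude that the main outcome is under-adjusted: baseline cognition is already a named covariate there.

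**What to change.** Add one sentence to the Biostatistical Analysis section, for example: *Each BDNF, gait, ERP and TCD measure will be analysed in its own ANCOVA-type model, which includes that measure's baseline value besides the planned background covariates.* Do not place all marker baselines in one joint MANCOVA. The change scores can stay as outcomes, since with the own baseline in the model the contrast is the same for change as for the post value. The cognitive analysis needs no change.

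No new data are needed, and no subject is lost, because a change score already requires the baseline. Each model gives up one degree of freedom: about 0.5% in variance at 200 subjects, 0.65% for TCD at 160, and about 1% to 1.4% if a marker is collected at one site only. Separate models also give no single joint test across the markers, so any such test would have to be specified apart. If an analysis plan already names these baselines, the sentence merely brings the protocol into line with it.

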### **Risks and Discomforts**

During the Intervention Programs only subjects whose primary care doctor indicate are safe to engage in in the physical exercise training program will be able to participate in the study (even if they are randomly assigned to one of the non-physical exercise intervention programs). In the physical exercise training program, perceived level of effort will be carefully monitored and subjects who report their perceived exertion to be hard will be instructed to decrease their level of effort. During the initial visit to the subject's home, the study staff will prepare a card that includes the name and phone number of the subject's PCP, in case medical issues arise.

During all of the structured intervention phases, study staff will be regularly communicating with participants to answer questions, address concerns, and try to augment a subject's level of comfort with the training activity.

Physical fitness training for 35 minutes, titrated to a moderate level of effort, is generally safe and often recommended for healthy adults. During exercise, there is a risk of fatigue, dyspnea, palpitations, and muscle cramps or aches. Following exercise, there is a risk of muscle, joint, or back discomfort. While exercising, individuals with heart disease are at risk for chest discomfort/angina.

Subjects will be told that if they experience symptoms, they should stop exercising. If they experience chest discomfort, they should contact their primary care physician. If the chest discomfort is severe, 911 emergency medical services should be called and the subject should be taken to a hospital emergency room for evaluation. For other symptoms, they should page the research team.

The PI, a physician, will review the symptoms with the subject and help determine whether further medical assessment is appropriate. As a safety measure, subjects can only participate in this study if approved by their primary care physician.

Cognitive training poses no serious clinical risks for participants. The cognitive exercises may cause some degree of frustration or fatigue. The subject may stop the testing at any time or decline to answer any question.

Awareness training poses no serious clinical risks for participants. It may make some individuals feel fatigued or frustrated.

During the interview, neuropsychological testing, and ERP paradigms, subjects may become anxious, frustrated, or fatigued. The study staff consists of trained individuals who will attempt to make subjects as comfortable as possible. Although it is hoped that subjects will answer all of the questions, they may

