### **Monitoring and Quality Assurance**

The Principal Investigator and Co-Investigators will report any and all serious and non-serious adverse events to the IRB within a timely manner.

Study personnel must immediately report to the PI any adverse events from this study. All adverse events will be reviewed by the PI and reported to the Partners Human Research Committee (HRC) in accordance with ICH Guidelines.

The PI will be responsible for monitoring and assuring the validity and integrity of all of the data, for monitoring the day-to-day activities of all study procedures, and for the adherence to the IRB-approved protocol. The PI will maintain a tracking log to reflect all adverse events regardless of relationship or expectedness and submit the updated log each year during the IRB renewal process.

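### Subjects are told to page the research team for exercise symptoms other than chest discomfort, and the protocol states no prompt notice to the team after chest discomfort itself

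*Protocol*

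**What the plan says.** The Risks and Discomforts section names the symptoms that home exercise may bring. For the session itself it says: "During exercise, there is a risk of fatigue, dyspnea, palpitations, and muscle cramps or aches". For the hours afterwards it adds muscle, joint and back complaints. For one group it goes further: "While exercising, individuals with heart disease are at risk for chest discomfort/angina". Subjects are told to stop exercising if they have symptoms. The section then says whom to turn to:

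- Chest discomfort: "If they experience chest discomfort, they should contact their primary care physician".
- Severe chest discomfort: "If the chest discomfort is severe, 911 emergency medical services should be called", followed by evaluation in an emergency room.
- Everything else: "For other symptoms, they should page the research team".

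The next paragraph says: "The PI, a physician, will review the symptoms with the subject and help determine whether further medical assessment is appropriate". Under Monitoring and Quality Assurance, "Study personnel must immediately report to the PI any adverse events from this study". The PI reviews all adverse events and keeps a log of them whatever their cause or expectedness.

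**The concern.** The word *other* attaches the page to every symptom except chest discomfort. Chest discomfort is also the only symptom with a 911 step, so it is the one the study physician would most want to hear about quickly. Sending the subject to the PCP or emergency services first is right. What is missing is the second step, telling the team afterwards.

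The setting makes this matter. Subjects are 65 or older and exercise in their own homes, 5 days a week for 5 weeks. Oversight of a possible cardiac event depends on someone in the study learning of it. If nobody does, PI review and entry in the adverse event log start late or not at all. This is a matter of safety oversight and does not touch sample size, error rates or any endpoint.

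**Working it through.** No arithmetic applies. The check is to ask, for each provision that could bring chest discomfort to the team's notice, whether it does so and how soon.

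1. **The routing rule (Risks and Discomforts).** The two chest discomfort instructions name the PCP, 911 and the emergency room. Neither mentions the team. The paging instruction follows and covers the remaining symptoms.

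2. **PI review (same section).** The sentence does not limit which symptoms it covers, so it can be read to include chest discomfort. It gives no route or timing by which chest discomfort would reach the PI. The instruction just before it supplies a route only for other symptoms.

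3. **Immediate reporting (Monitoring and Quality Assurance).** The duty falls on study personnel. It starts once they know of the event and places no duty on the subject, the PCP or an emergency room.

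4. **The card left in the home (Risks and Discomforts).** It is described as carrying the PCP's name and telephone number for use if a medical problem arises. No team contact is mentioned.

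5. **The PCP (Permission to Contact a Potential Subject's PCP).** The fax number is provided for returning the clearance form before enrolment. No later report from the PCP to the team is described.

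6. **Contact started by the subject (Interventions – General Features and Overview).** Subjects are encouraged to get in touch at any time with a question or concern. This is voluntary and general, whereas the routing rule is specific and points chest discomfort elsewhere.

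7. **Weekly contact (same section, and the physical exercise section).** A team member calls or emails each week to give feedback and deal with questions. It is not described as asking about symptoms. An event may come up here, but nothing ensures it.

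8. **Data monitoring (same two sections).** Training data are watched for breaks. For the exercise arm, the accelerometer is to be connected for upload at least once a week, and no interval is given for session data. A gap in training may prompt a call sooner than the weekly contact, but it does not itself show the reason.

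**Result.** Items 6 to 8 are the routes left. The time until the team knows is:

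- 0 days, if the subject or someone for them calls at once;
- up to about 7 days, if the subject waits for the next weekly contact and raises the event then;
- longer, with no limit set by the text, if the event is not mentioned at that contact.

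The protocol gives no rate of chest discomfort, so the number of late or missed reports cannot be estimated.

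**The case against.** The best counter-argument is that these sentences tell a subject whom to ask for help and are not a reporting rule. Adverse event capture is set elsewhere, applies to all events and excludes none. PI review is worded without restriction. Subjects hear from the team weekly and may call at any time, and someone sent to a doctor by study exercise would plainly have a concern to raise. Instructions to subjects also belong in the consent form and training materials, and the consent pages are not in the document available here.

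Much of this stands. The order of care is right, routes to the team exist, no two sections conflict, and a notice may be present in the consent form. PCP clearance and the exclusion of heart disease that would prevent exercise make the event less likely. What does not stand is that these provisions close the gap: the reporting duty needs prior knowledge, and the other routes are voluntary or weekly.

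Three stronger readings are tempting and should be resisted:

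- A reader might infer that the delay is capped at about 7 days. It is not, because the weekly contact is not described as a symptom enquiry.
- A reader might count that five of six listed symptom items lead to a page and treat this as a measure of the problem. The count depends on how the items are grouped and measures neither risk nor delay.
- A reader might infer that the protocol keeps chest discomfort from the team, or that care is withheld. Nothing forbids telling the team, and care is directed first.

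**Conclusion.** The point holds as a defect in a stated safety instruction. The rule asks for a page after minor symptoms and asks for none after chest discomfort, and no other section shown supplies a prompt notice. PI review and adverse event reporting of such an event therefore rest on the subject volunteering it or on its coming up at the next weekly contact.

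The consequence is limited to delayed or missed safety oversight, as set out in the check. The conclusion assumes that subjects follow the instruction as written, and it covers only the protocol text; if the consent form or subject materials already ask for a page, the protocol needs only to be brought into line. The change should be made because it is cheap and the event is potentially serious.

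**What to change.** Leave the PCP and 911 routes as they are and add one sentence to Risks and Discomforts, repeated in the subject instructions:

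> Once care has been sought, the subject (or someone for them) also pages the research team the same day for any chest discomfort.

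The cost is one sentence and a few more pages for the team to answer.

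A pause in training until the PCP or treating physician clears the subject is a reasonable optional addition, at the price of a short interruption for anyone affected. A further requirement that the PI agree before training resumes does not follow from this point: what has been shown is a gap in notification.

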## Detailed Protocol: SAGE

Subjects will be recruited at the two sites with the aim of obtaining a representative sample of healthy, elderly participants 65 and older in each country. At BWH, subjects will be recruited through several channels, including announcements in local newspapers and other available media; outreach to independent living communities; senior activity centers and organizations; and through existing databases for studies of healthy aging that exist at BWH.

To be included in the study, participants must:

1. Be 65 or older
2. Have  $\geq 8$  years of education
3. Be sufficiently fluent in the English language to understand instructions and perform the neuropsychological tests (as the purpose of the project is to study healthy aging)
4. Score above levels indicating possible cognitive impairment on the Mini Mental State Exam (MMSE) ( $\geq 26$ ) [87]
5. Have an estimated intelligence quotient (IQ) score  $\geq 90$  based on the American National Reading Test (AmNART) [88]
6. Have a score within 2 SD of the age-appropriate mean on the short form of the Boston Naming Test [89, 90]
7. Have a score within 2 SD of the age-appropriate mean on the Logical Memory Subtest of the Wechsler Memory Scale—Third Edition [91]

Subjects will be excluded for any of the following reasons:

1. History of CNS diseases or major psychiatric disorders based on DSM-IV criteria [92]
2. Score of  $> 10$  on the Geriatric Depression Scale [93]
3. Corrected visual acuity worse than 20-50 as tested by a Snellen wall chart
4. Severe hearing disability that would interfere with their ability to participate in the experiments (e.g., to hear instructions and participate in cognitive testing)
5. Medical conditions (e.g., heart or pulmonary disease) that would prevent them from participating in the physical exercise training program
6. Evidence of substantial functional decline based on interview questions and completion of a questionnaire based on the Clinical Dementia Rating Scale [94] by an informant who knows the subject well

Permission will be obtained from subjects to contact their primary care physicians (PCPs). PCPs will be asked to confirm that if their patient were assigned to the physical training condition, he/she could safely participate. Subjects will be excluded if their PCP does not confirm that they can safely participate.

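### The exercise symptom instruction gives a 911 route only for severe chest discomfort; breathlessness and palpitations go to the research pager however severe

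*Protocol*

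**What the plan says.** The section Risks and Discomforts first lists what may happen during exercise: "there is a risk of fatigue, dyspnea, palpitations, and muscle cramps or aches". It adds chest discomfort or angina for people with heart disease. The instruction to subjects then has four parts:

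- Any symptom: "Subjects will be told that if they experience symptoms, they should stop exercising".
- Chest discomfort: "If they experience chest discomfort, they should contact their primary care physician".
- Severe chest discomfort: "If the chest discomfort is severe, 911 emergency medical services should be called", followed by transfer to an emergency room.
- Everything else: "For other symptoms, they should page the research team".

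A new paragraph says that the PI, who is a physician, "will review the symptoms with the subject and help determine whether further medical assessment is appropriate". Earlier in the section, staff at the first home visit "will prepare a card that includes the name and phone number of" the subject's PCP.

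Related safeguards stand elsewhere. Under Subject Selection, medical conditions (heart or pulmonary disease are the examples) that would prevent participation in the exercise program are an exclusion, and "Subjects will be excluded if their PCP does not confirm that they can safely participate". The description of the exercise program provides exertion check-ins every 3-4 minutes and a Pause control, and tells subjects not to work to the point of dizziness or breathlessness. The overview of the interventions provides weekly staff contact, an open invitation to get in touch, and monitoring of the data for interruptions.

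**The concern.** The instruction separates mild from severe for one symptom only. Dyspnea and palpitations are foreseen risks of the program, and either can be an emergency when severe, but both fall into the catch-all that leads to the pager. Subjects are 65 or older and train in their own homes. Staff are stated to be present for a practice run, and no staff presence is described for later sessions. Someone who stops because of severe breathlessness and then follows the instruction pages the team and waits for a review of symptoms, when a direct emergency call may be needed. What is at stake is delay.

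There is a smaller, separate gap. Neither chest discomfort instruction asks the subject to let the team know. Monitoring and Quality Assurance requires study personnel to report adverse events to the PI at once, but they can report only what has reached them.

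**Working it through.** No arithmetic applies beyond a count, and the protocol states no figure to reproduce. The check sets each symptom against the route that the instruction gives it once exercise has stopped.

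| Symptom | Listed as an exercise risk? | Route if mild | Route if severe |
|---|---|---|---|
| Chest discomfort | Yes, for people with heart disease | PCP | 911 and emergency room |
| Dyspnea | Yes | Pager | Pager |
| Palpitations | Yes | Pager | Pager |
| Fatigue, muscle cramps or aches | Yes | Pager | Pager |
| Fainting | No (named only for the blood draw) | Pager | Pager |

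1. Routes stated: PCP, 911 and pager, so 3.
2. Symptoms with a 911 route: severe chest discomfort, so 1. The protocol mentions 911 nowhere else.
3. Listed risks that can be emergencies when severe and that go to the pager at every severity: dyspnea and palpitations, so 2.
4. Could another provision supply the missing route?
   - PCP clearance and the exclusions act before enrolment.
   - Check-ins, Pause and the stop rule reduce or end exertion.
   - The card is stated to carry the PCP's details.
   - The invitation to contact the team covers general questions and concerns.
   - The PI's review follows the page.

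   Each lowers the risk or its consequences. None tells a subject to seek emergency care for a severe symptom other than chest discomfort.
5. How would the team learn of chest discomfort? The subject may mention it unprompted, it may come up at the weekly call or email, or a break in the training data may be noticed. No instruction asks for it to be reported.

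**The case against.** The best defence is that the section lists ordinary effects of moderate exercise and never speaks of severe dyspnea or severe palpitations. The severity tier is brought in from outside. Nothing forbids a 911 call, subjects are screened as cognitively intact (MMSE of at least 26), and the pager leads to a physician who can send them for care. The instruction covers one of four arms for five weeks. It also summarises what subjects will be told, and the consent form matched to the assigned condition was removed before review.

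Much of this stands, and it limits the point. A reader might infer that subjects are directed away from emergency care, or that nothing else protects them. The protocol supports neither: no sentence discourages a 911 call, and the safeguards are real. Nor can the protocol show what the consent form says. What survives is narrow. The catch-all has no severity exception, although its authors did make one for chest discomfort, and a safety instruction should not depend on subjects departing from it.

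A reader might also infer that chest discomfort bypasses the PI altogether. That goes too far. The sentence on PI review refers to symptoms generally and may include chest discomfort, and weekly contact and data monitoring could bring it to light. The shortfall is a possible reporting lag. Sending the subject to the PCP or 911 first is the right order.

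**Conclusion.** The point holds as a minor improvement to safety wording. The instruction attaches 911 to one symptom out of those it foresees, and leaves two potentially urgent ones with the pager at any severity. The size of the harm cannot be given: the protocol states no event rate and no paging response time, and none is assumed here. The conclusion rests on reading the catch-all literally and on the protocol text alone. Consent wording and the Swedish site's instructions are not shown and may already close the gap.

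Three stronger demands might seem to follow, but the text does not support them. Sending every severe symptom to 911 would include a severe muscle cramp. A joint PI and PCP rule for resuming training would be a new procedure beyond the defect. Adding falls to the risk list is unrelated to this instruction, and the program already offers low-impact, seated and chair-supported exercise. No outcome, sample size or analysis is affected.

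**What to change.** In Risks and Discomforts and in the matching subject instructions, tell subjects to stop and call 911 for severe chest discomfort, severe or persistent shortness of breath, severe or persistent palpitations, or fainting. Keep the PCP route for milder chest discomfort and the pager for other, milder symptoms.

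Secondarily, add that after contacting the PCP or 911 the subject should promptly tell the research team about any chest discomfort, so that the PI's review and adverse event reporting can take place.

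The cost is a few sentences, plus some extra 911 calls or pages for symptoms that prove benign. The exercise program, eligibility rules and analysis stay as they are.
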